### Step 3:

To assess the robustness of the analyses for deviations from ignorable censoring the last step will be repeated after inflating the hazards for rivaroxaban/aspirin follow-up non-completers in the rivaroxaban groups. The hazards in the control group will not be inflated, that is, for these subjects, rivaroxaban/aspirin follow-up non-completion will be treated as ignorable. Thereafter, the multiple imputation described above will be repeated with the inflated hazards.

The inflation factor be increased stepwise to determine the factor F, for which the upper limit of the 95%-CI for the HR for rivaroxaban 2.5 mg bid + aspirin 100 mg od relative to rivaroxaban placebo + aspirin 100 mg od crosses 1 – the “tipping-point” – and the factor G, for which the upper limit of the 95%-CI for the HR for rivaroxaban 5 mg bid + aspirin placebo od relative to rivaroxaban placebo + aspirin 100 mg od crosses 1.

The following inflation factors will be considered: 10% to 200% increased by 10% steps, 200% to 500% increased by 50% steps and 500% to 1000% increased by 100% steps.

The sensitivity analysis described in this section will be repeated using a Weibull survival model fitted to all randomized subjects and adjusted for treatment groups, stratification factor and the baseline covariates described above.

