This SAP contains definitions of analysis sets, key derived variables, and statistical methods for analysis of efficacy and safety for the COMPASS study. It provides a technical and detailed elaboration of the principal features of the planned analyses, e.g., censoring schemes for time-to-event variables. Amendments and/or appendices to this SAP may be used to provide more details on the coding guidelines, data-handling, and output tables and figures. These SAP-associated documents will be finalized ideally 6 months before the planned study end to take into account emerging data external to the trial becoming available during conduct of the trial that could influence study interpretation. All SAP associated documents will be finalized without knowledge of any emerging results by treatment group from the trial.

An amendment of the integrated SAP, Version 3.0, became advisable based on a recommendation received from the DSMB to the Study Chair and Co-Principal Investigators, dated February 06, 2017. The DSMB recommended that treatment arms rivaroxaban 2.5 mg bid + aspirin 100 mg daily, rivaroxaban 5.0 mg bid, and aspirin 100 mg daily be stopped as soon as an orderly close-out of this portion of the COMPASS study could be carried out. The DSMB made this recommendation because they found upon performing the first interim analysis that one of the rivaroxaban arms reached the critical value for early efficacy, as outlined in the DSMB charter. Therefore, the Steering Committee decided to stop the rivaroxaban/aspirin arms of the study for overwhelming efficacy.

The SAP Amendment v3.1, integrated in SAP, Version 4.1, was written fully blinded to the treatment allocation with the intent to fully preserve the statistical analyses that have been outlined in the protocol and the previous version of the SAP. It seeks to clarify some aspects pertaining to the interim analysis and to reflect the wording and additional close-out visits prompted by the premature stop of the anti-thrombotic study treatment arms. In addition, it includes a detailed description of the sensitivity analyses planned to explore the potential impact of missing data on the primary analysis.

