#### Step 1 (Family 1):

The two dose-placebo comparisons in Family 1 (Hypotheses  $H_{1A}$  and  $H_{1B}$ ) will be performed using a truncated Hochberg test with the pre-specified truncation parameter  $\gamma = 0.9$  at  $\alpha=0.05$ . Consider the null hypotheses  $H_{1A}$  and  $H_{1B}$  and their associated raw p-values  $p_{1A}$  and  $p_{1B}$ .

- (a) If  $\max(p_{1A}, p_{1B}) \leq \alpha (1+\gamma)/2 = 0.0475$ ,  
then reject both hypotheses  $H_{1A}$  and  $H_{1B}$  and continue with Step 2a.
- (b) If  $\max(p_{1A}, p_{1B}) > \alpha (1+\gamma)/2 = 0.0475$  and  
 $\min(p_{1A}, p_{1B}) \leq \alpha/2 = 0.025$ ,  
then accept  $H_{1k}$ , for all  $i = 1,2,3,4$  where  $k \in \{A,B\}$  corresponds to the hypothesis yielding the larger of the two p-values and reject  $H_{1j}$ , where  $j \in \{A,B\}$  corresponds to the hypothesis yielding the smaller of the two p-values and continue with Step 2b.
- (c) If  $\max(p_{1A}, p_{1B}) > \alpha (1+\gamma)/2 = 0.0475$  and

$\min(p_{1A}, p_{1B}) > \alpha/2 = 0.025$ ,  
then accept  $H_{ik}$ , for all  $i = 1,2,3,4$  and all  $k = A,B$  and stop.

Step 2 (Family 2):

The overall significance level used in Family 2 is determined by the number of significant tests in Step 1. If both null hypotheses  $H_{1A}$  and  $H_{1B}$  are rejected in Step 1, continue with Step 2a. If only one null hypothesis is rejected in Step 1, the corresponding null hypothesis will be tested according to Step 2b.

Step 2a:

The two dose-placebo comparisons in Family 2 (Hypotheses  $H_{2A}$  and  $H_{2B}$ ) will be performed using a truncated Hochberg test with the pre-specified truncation parameter  $\gamma$  at the full  $\alpha=0.05$ . Consider the null hypotheses  $H_{2A}$  and  $H_{2B}$  and their associated raw p-values  $p_{2A}$  and  $p_{2B}$ .

- (a) If  $\max(p_{2A}, p_{2B}) \leq \alpha(1+\gamma)/2 = 0.0475$ ,  
then reject both hypotheses  $H_{2A}$  and  $H_{2B}$  and continue with Step 3a.
- (b) If  $\max(p_{2A}, p_{2B}) > \alpha(1+\gamma)/2 = 0.0475$  and  
 $\min(p_{2A}, p_{2B}) \leq \alpha/2 = 0.025$ ,  
then accept  $H_{ik}$ , for all  $i=2,3,4$ , where  $k \in \{A,B\}$  corresponds to the hypothesis yielding the larger of the two p-values and reject  $H_{2j}$ , where  $j \in \{A,B\}$  corresponds to the hypothesis yielding the smaller of the two p-values and continue with Step 3b.
- (c) If  $\max(p_{2A}, p_{2B}) > \alpha(1+\gamma)/2 = 0.0475$  and  
 $\min(p_{2A}, p_{2B}) > \alpha/2 = 0.025$ ,  

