### 6.2.1.2 Primary Efficacy Analysis

Analysis of the primary efficacy outcome will be based on the intention-to-treat principle. Two comparisons will be performed to compare each of the rivaroxaban-based treatment groups to the common aspirin-control group to evaluate:

- Superiority of rivaroxaban 2.5 mg bid + aspirin 100 mg od over rivaroxaban placebo + aspirin 100 mg od (control)
- Superiority of rivaroxaban 5 mg bid + aspirin placebo over rivaroxaban placebo + aspirin 100 mg od (control).

The primary null hypothesis  $H_{0;riva2.5}$ :

“There is no difference between the rivaroxaban 2.5 mg bid + aspirin 100 mg od treatment group and the rivaroxaban placebo + aspirin 100 mg od (control) in the probability of the primary efficacy outcome for all time points  $t \geq 0$  relative to randomization.”

will be tested against the alternative hypotheses  $H_{1;riva2.5}$ :

“There is a difference between the rivaroxaban 2.5 mg bid + aspirin 100 mg od treatment group and the rivaroxaban placebo + aspirin 100 mg od (control) in the probability of the primary efficacy outcome for at least one time point  $t \geq 0$  relative to randomization.”

The corresponding primary null hypothesis  $H_{0;riva5}$  will be tested comparing rivaroxaban 5 mg bid + aspirin placebo treatment with rivaroxaban placebo + aspirin 100 mg od (control). Statistical testing will be performed by a comparison of the “survival functions”  $S(t)$ , i.e., the probability that “time from randomization to the first occurrence of the following primary efficacy outcomes” is  $> t$ , for a time  $t$  relative to randomization.

The 2 comparisons will be performed using two separate stratified log-rank tests. Proton pump inhibitor use (3 strata levels: not randomized to a proton pump inhibitor; pantoprazole 40 mg od; pantoprazole placebo) will be used as a stratification factor in the statistical analysis. Study center will not be used as a stratification factor in the statistical analysis.

Following the mixture gatekeeping procedure as mentioned in Section 6.2, a truncated Hochberg test with the pre-specified truncation parameter  $\gamma = 0.9$  at  $\alpha=0.05$  will be used.

There will be no formal comparison between the rivaroxaban 2.5 mg bid + aspirin 100 mg od and rivaroxaban 5 mg bid + aspirin placebo groups.

---

 Text modified as per modification 1 in integrated SAP, Version 4.1.

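### The missing-data tipping factors F and G are read at p = 0.05, a level at which the truncated Hochberg primary test never rejects; the gap matters only for a stronger arm that stands alone

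*SAP*

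**What the plan says.** SAP Section 10.4.3 Step 3 inflates the imputed hazards of follow-up non-completers in the rivaroxaban groups and leaves control alone: "The hazards in the control group will not be inflated". The inflation rises stepwise "to determine the factor F, for which the upper limit of the 95%-CI for the HR for rivaroxaban 2.5 mg bid" plus aspirin, relative to aspirin alone, crosses 1. The other comparison has "the factor G, for which the upper limit of the 95%-CI for the HR for rivaroxaban 5 mg bid + aspirin placebo od", with the same criterion. The grid runs to 1000%, in 100% steps above 500%.

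The primary hypotheses are decided differently. Section 6.2.1.2 states: "Following the mixture gatekeeping procedure as mentioned in Section 6.2, a truncated Hochberg test with the pre-specified truncation parameter" of 0.9 at a level of 0.05. Under Section 6.2, Step 1 (Family 1), both nulls are rejected if the larger p-value is at most "\alpha (1+\gamma)/2 = 0.0475". Otherwise only the hypothesis with the smaller p-value can be rejected, and its bound is "\leq \alpha/2 = 0.025".

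Section 1 records that at the first interim analysis "one of the rivaroxaban arms reached the critical value for early efficacy". Section 10.4 does not tie F or G to the Section 6.2 thresholds and does not label them descriptive.

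**The concern.** Section 10.4 presents this analysis as a check on how missing data might affect the primary efficacy analysis, and a tipping point is normally read as the departure from ignorable censoring that overturns the conclusion. Here the tipping criterion and the decision criterion differ. There is a range of inflation over which the primary null would no longer be rejected while the sensitivity analysis still reports that nothing has tipped. The mismatch can run only one way, towards greater apparent robustness. The one-arm case, where the gap is widest, is realistic: the same SAP version reports that one arm had crossed the interim boundary, and inflating both rivaroxaban groups pushes both p-values up.

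**Working it through.** **Inputs.** α = 0.05 and γ = 0.9 (Sections 6.2 and 6.2.1.2); truncated Hochberg formula for m = 2 (Appendix 10.3); expected events 826 control and 687 per rivaroxaban arm, hence 1,513 per comparison (Section 4.4); about 1,100 events in three arms at the first interim (Section 4.4), hence about 1,100 × 2/3 = 733 per comparison; 9,134 subjects per arm (Section 7).

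**1. The plan's own figures.** Both arms: (0.9 + 0.1/2) × 0.05 = 0.0475. One arm alone: 0.05/2 = 0.025. Both match Section 6.2. As a check that the rule is read as intended, the expected events give HR = ln(1 − 687/9,134)/ln(1 − 826/9,134) = 0.825 with SE = √(1/826 + 1/687) = 0.052. Applying the rule to two correlated normal statistics (correlation 0.45 to 0.50 from the shared control) gives power of 98.3–98.5% for at least one arm and 92.7–92.8% for both. Table 7-3 has 98.27% and 92.97%.

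**2. Levels side by side.**

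| Criterion | Two-sided p | Critical z | Matching CI |
|---|---|---|---|
| F and G as written | 0.05 | 1.960 | 95% |
| Primary test, both arms rejected | 0.0475 | 1.982 | 95.25% |
| Primary test, one arm alone | 0.025 | 2.241 | 97.5% |

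No primary null can be rejected with p between 0.0475 and 0.05. None can be rejected with p between 0.025 and 0.0475 unless the other arm is also at or below 0.0475.

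**3. Which level binds which arm.** The arm with the larger p-value is rejected only through the 0.0475 rule, so its relevant comparison is 1.960 against 1.982. The 0.025 rule can bind only the arm with the smaller p-value, once the other has passed 0.0475. If the stronger arm's |z| is then still above 2.241 (a lead of more than 2.241 − 1.982 = 0.259), it is lost at 2.241. With a smaller lead it is lost somewhere between 1.982 and 2.241.

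**4. Distance to tipping, in standard errors of log HR.**
- Stronger arm alone, Z = 4.0: (4.0 − 1.960)/(4.0 − 2.241) = 2.04/1.76 = 1.16.
- Stronger arm alone, Z = 3.0: 1.04/0.76 = 1.37. Z = 2.5: 0.54/0.26, about 2.1.
- Weaker arm, Z = 3.0: 1.04/1.018 = 1.02. Z = 2.5: 0.54/0.518 = 1.04.

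**5. On the hazard-ratio scale.** With critical HR = exp(−2z/√events), 1,513 events give 0.904 (as written), 0.903 (both arms) and 0.891 (one alone). About 733 events give 0.865, 0.864 and 0.847. When a lone arm loses significance at p = 0.025, its upper 95% limit is exp(−2 × (2.241 − 1.960)/√events) = 0.986 with 1,513 events or 0.979 with 733, so Step 3 would not yet record a tipping point.

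**6. Illustrative inflation.** The SAP gives neither the missing fraction nor an observed Z, so these are assumptions: missing person-time m = 1%, and imputed hazard 1.5 times the arm's own. With observed events c (control) and t (active) and q = 1.5 × m/(1 − m), solve ln(C/T)/√(1/C + 1/T) = critical z, where C = c(1 + q) and T = t(1 + q × multiplier). The first figure in each cell is for 1,513 events, the second for 733.

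| Observed Z of a lone stronger arm | Inflation at p = 0.05 | Inflation at p = 0.025 |
|---|---|---|
| 4.0 | +773% to +1,161% | +665% to +999% |
| 3.0 | +385% to +569% | +282% to +417% |
| 2.5 | +200% to +293% | +99% to +145% |

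The range is wide: at Z = 4 and 1,513 events, 0.5% missing gives +1,536% against +1,321%, and 2% missing gives +391% against +338%.

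**The case against.** The strongest reply has four parts.

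- **Convention.** Section 6.2 makes 95% the default interval, Section 6.2.1.2 reports the primary hazard ratios with unadjusted 95% intervals, and Step 3 names that interval explicitly. This explains the choice but does not cure it. The default governs how intervals are displayed; the decision level for the primary hypotheses is set separately by the truncated Hochberg rule.
- **Not an exact replica anyway.** The decision uses a stratified log-rank test, whereas the tipping analysis pools Cox estimates. That is true, but it is no reason to add a known difference in level.
- **Exploratory standing.** The analysis is introduced under Section 6.2.7, trial success rests on the totality of evidence, and no rejection depends on F or G. This stands and limits the importance of the point.
- **Size.** At Z near 4 the illustrated difference is one or two grid steps between very large inflations, and most readers would judge robustness the same way. This also stands.

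A reader might infer that F and G are both materially overstated, or that the 37% and roughly twofold figures describe this trial. The documents do not support that. The 0.025 level cannot bind the weaker arm, whose distance changes by only 2–4% at Z of 3.0 or 2.5. The arm that makes the one-arm case realistic is the one that met a boundary of 4 standard deviations at the interim, where the figure is 16%. The larger figures would need that stronger arm to stand at a Z of 3.0 or 2.5 at the cut-off. This is possible if the effect had shrunk, but nothing in the SAP states it.

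**Conclusion.** The point holds, with limited size. As written, F and G sit at or beyond the inflation at which the primary conclusion is lost, never short of it. For the weaker arm, or while both arms stay significant, the gap is trivial (1.960 against 1.982). For a stronger arm standing alone it is material (1.960 against 2.241): distance to tipping is overstated by about 16% in standard errors if its Z is near 4, and by more only if its Z is lower. The direction and the critical values follow from the SAP alone. The inflation percentages rest on an assumed missing fraction and imputed hazard, so the actual shift in F cannot be computed from the documents. It would also be wrong to conclude that the primary test is compromised: its type I error is unaffected, because only a sensitivity analysis is involved.

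**What to change.** In Section 10.4.3 Step 3, define F and G by the primary decision rule. At each inflation step, take the pooled p-values of both comparisons at that same inflation, apply Step 1 (Family 1) of Section 6.2 to the pair, and report for each arm the smallest inflation at which its primary null is no longer rejected. State that an arm not rejected without inflation has no tipping factor. Keep the 95% interval crossing as a descriptive addition, labelled as such.

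The rule belongs after the PROC MIANALYZE step in Section 10.4.6, where the combined inference is produced. Changing the ALPHA option in PROC PHREG would not do it, because the applicable level can switch along the grid as the other arm's p-value rises.

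The cost is a sentence or two of text and a small joint rule across the two models in the code. The same imputed data sets serve, so no new imputation is needed. The only other downside is slightly smaller reported tipping factors.

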### 10.4.4 Parameter estimation

For subjects who prematurely discontinued any anti-thrombotic study treatment, a Weibull survival model will be fitted to estimate the hazard of a primary outcome event at the last contact date in the rivaroxaban/aspirin portion of the trial:

```
PROC LIFEREG DATA = <dataset> OUTEST=<dataset1>;
  MODEL ttevalue*ttecnsr(1) = trtgrp stratum <covariates> /
    DISTRIBUTION = weibull INTERCEPT=8 INITIAL=0.2;
  OUTPUT OUT=<dataset2> CDF=cdf XBETA=xbeta;
RUN;
/*
where
dataset = name of sub-dataset including all ITT subjects who prematurely
discontinued any anti-thrombotic study treatment
dataset1 = SAS data set containing the parameter estimates
dataset2 = SAS data set containing statistics (CDF and x'β) calculated after
fitting the model
ttevalue = time to first occurrence of primary efficacy outcome event
ttecnsr = censoring index (1 = right-censored, 0 = event)
trtgrp = variable coding randomized antithrombotic treatment group
        (0 = control group, 1 = rivaroxaban 2.5 mg + aspirin 100 mg)
stratum = variable for PPI stratification factor (three levels)
*/
```

The SAS LIFEREG procedure will be used to model the natural logarithm  $w = \log(t)$  of the survival time. The survival function used by SAS has the form

$$S(w) = \exp\left(-\exp\left(\frac{w-\mu}{\sigma}\right)\right),$$

where  $\mu$  is the location parameter and  $\sigma$  the scale parameter.

Re-parameterization by  $\lambda = \exp(\mu)$  and  $\beta = 1/\sigma$  results in the survival function  $S_1$  with

$$S(w) = S_1(t) = \exp\left(-\left(\frac{t}{\lambda}\right)^\beta\right).$$

The estimated hazard at the last contact date in the rivaroxaban/aspirin portion of the trial will be obtained from the fitted Weibull model, adjusted for treatment and baseline covariates for each subject.

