## 6.2.1 Primary Efficacy

### 6.2.1.1 Primary Efficacy Variable

The primary efficacy variable is the time (in days) from randomization to the first occurrence of the following primary efficacy outcome events:

- Myocardial infarction
- Stroke
- Cardiovascular death

All unrefuted primary efficacy outcome events within the data scope according to intention-to-treat principle (see Section 4.5.2) will be considered for the derivation of the primary efficacy variable.

- For those subjects with documentation of an unrefuted primary efficacy outcome event occurring  
after the date and time of randomization and up until the minimum (earliest) of the global rivaroxaban/aspirin outcomes cut-off date and the subject's last contact date during the rivaroxaban/aspirin portion of the study

time (in days) from randomization to the first occurrence of the primary efficacy outcome will be derived as:

- the date of the subject's first primary efficacy outcome event  
– the randomization date + 1.

This will constitute an uncensored observation.

- For those subjects without documentation of an unrefuted primary efficacy outcome event within the data scope according to intention-to-treat principle, time (in days) from randomization to the first occurrence of the primary efficacy outcome will be derived as:

 Text modified as per modification 1 in integrated SAP, Version 3.0.

 Text modified as per modification 1 in integrated SAP, Version 3.0.

 Text modified as per modification 1 in integrated SAP, Version 4.1.

 Text modified as per modification 1 in integrated SAP, Version 3.0.

- the minimum (earliest) of {the global rivaroxaban/aspirin outcomes cut-off date, the subject's last contact date during the rivaroxaban/aspirin portion of the study} – the randomization date +1.

This will constitute a right-censored observation.

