**Table 10-2. Definition of sensitivity analysis subject characteristics**

Subgroups	Definition
Rivaroxaban/aspirin follow-up non-completer	Subjects alive for whom 
 
• the last contact date during rivaroxaban/aspirin portion of the study is before the global rivaroxaban/aspirin outcomes cut-off date.
 

Rivaroxaban/aspirin follow-up completer	Subjects for whom 
 
• the last contact date during rivaroxaban/aspirin portion of the study is at or after the global rivaroxaban/aspirin outcomes cut-off date
 
• subject died
 

Rivaroxaban/aspirin study treatment non-completer	Subjects 
 
• who are rivaroxaban/aspirin follow-up non-completers and/or
 
• whose date of last rivaroxaban/rivaroxaban placebo or date of last aspirin/aspirin placebo study treatment is before the global rivaroxaban/aspirin outcomes cut-off date or before the subject’s death date (whatever comes first)
 

Rivaroxaban/aspirin study treatment completer	Subjects 
 
• who are rivaroxaban/aspirin follow-up completers and
 
• whose date of last rivaroxaban/rivaroxaban placebo and date of last aspirin/aspirin placebo study treatment is at or after the global rivaroxaban/aspirin outcomes cut-off date or identical to the death date
 

Note: the follow-up definitions from [Table 10-2](#) do not depend on

- premature discontinuation of study medication,

- the experience of an unrefuted primary efficacy outcome (rivaroxaban/aspirin follow-up non-completers may have experienced an unrefuted primary efficacy outcome event before premature discontinuation of their rivaroxaban/aspirin follow-up. However, only rivaroxaban/aspirin follow-up non-completers for whom no unrefuted primary efficacy outcome event is documented might impact the primary analysis due to missing outcome information.) and/or
- the reasons for being a rivaroxaban/aspirin follow-up non-completer, for example “complete withdrawal of informed consent”, “lost to follow-up”, or “other”.

Subjects who died are considered rivaroxaban/aspirin follow-up completers and having no missing outcome information, because subjects who experienced a terminal event cannot be followed-up.

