**Figure 10-1 Subdivision of ITT set for estimation of individual hazards for imputation**

**Step 1:**

According to the study protocol all subjects are to be followed until the end of the rivaroxaban/aspirin follow-up / end of the study and data on the primary efficacy outcomes are collected irrespective of whether or not a subject is on or off anti-thrombotic treatment. The cohort of subjects who prematurely discontinue any anti-thrombotic study treatment (i.e. either study

rivaroxaban bid and/or study aspirin treatment) will be used for imputation of unobserved follow-up time.

More specifically, for subjects who prematurely discontinued any anti-thrombotic study treatment, a Weibull survival model will be fitted to estimate the individual hazard of a primary outcome event at the last contact date of the rivaroxaban/aspirin portion of the trial. The model will be adjusted for treatment groups (rivaroxaban 2.5 mg bid + aspirin 100 mg od, rivaroxaban 5 mg bid + aspirin placebo od, rivaroxaban placebo + aspirin 100 mg od), stratification factor (not randomized to a proton pump inhibitor; pantoprazole 40 mg od; pantoprazole placebo) and the following baseline covariates:

- CAD and PAD, CAD only, PAD only
- Age (<65, 65 years or older)
- Region (North America, Western Europe, Eastern Europe, Asia Pacific and other, and South America)
- History of a prior heart failure
- History of prior stroke
- History of prior MI

The imputation model will also include a covariate indicating the occurrence of a major bleeding event (post-randomization event), if the bleeding occurred (start date) during the 90 days preceding the unrefuted primary efficacy outcome event or the censoring date relevant for primary analysis:

If the individual hazard for a subject cannot be estimated from the above model due to missing covariates the hazard estimate from a crude model – adjusted for treatment groups and stratification factor only – will be used for this subject (see Section 10.4.4).

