### Step 2:

For subjects with missing rivaroxaban/aspirin follow-up time who did not experience an unrefuted primary outcome event and were alive at censoring, random variables reflecting a subject's individualized hazard (from step 1) will be simulated using the conditional time to event distribution after the last available rivaroxaban/aspirin follow-up (see Section 10.4.5). If this randomly generated variable has a value less than the elapsed time between the last available rivaroxaban/aspirin follow-up date (exclusive) and the "global rivaroxaban/aspirin outcomes cut-off date" (inclusive), the subject will be treated as having an primary efficacy event occurring at the date of last available rivaroxaban/aspirin follow-up plus the value from the random variable. Otherwise, the subject is re-adjusted to be censored at the "global rivaroxaban/aspirin outcomes cut-off date". Events and time at risk is imputed assuming that no death due to non-CV causes occurs.

Imputed events and event-free time at risk will be added to the observed events and times under risk in the study and the primary efficacy analysis will be repeated: The Cox proportional-hazards models from primary efficacy analysis will be fitted to the imputed data sets. This imputation and

---

 Experience shows that exponential distribution adequately models the survival time. In case of deviating data this approach can easily be extended to Weibull distribution by estimating the scale parameter  $\sigma$ .

analysis of primary outcome events will be repeated 1,000 times. Inferences for combined parameters will be done using multiple imputation rules that reflect imputation uncertainty (see Section 10.4.6).

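### The main missing-data imputation model borrows its hazard from subjects selected for later stopping drug, on a clock that starts at randomization, so F and G are not multiples of the post-discontinuation hazard

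*SAP*

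**What the plan says.** Appendix 10.4.3, Step 1, names the donors: "The cohort of subjects who prematurely discontinue any anti-thrombotic study treatment". Section 10.4.4 repeats this ("For subjects who prematurely discontinued any anti-thrombotic study treatment, a Weibull survival model will be fitted to estimate the hazard"), and its code comment describes the input file as "dataset = name of sub-dataset including all ITT subjects who prematurely" discontinued drug, with no further condition. The time variable is "ttevalue = time to first occurrence of primary efficacy outcome event", the same variable as in the primary analysis. Section 6.2.1.1 fixes its origin: "The primary efficacy variable is the time (in days) from randomization to the first occurrence of the following primary efficacy outcome events". No entry time, landmark at the stop or exclusion of events before the stop is given.

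The recipients are different. Step 2 and Section 10.4.5 take subjects who are alive and without a primary event at censoring, and simulate forward from their last contact, conditional on being event-free until then. Step 3 inflates these hazards stepwise in the rivaroxaban arms only, to find the factors F and G at which the upper 95% limit of the hazard ratio crosses 1. Step 3 also repeats the exercise with a Weibull model fitted to all randomized subjects.

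On pooling, Step 2 promises: "Inferences for combined parameters will be done using multiple imputation rules that reflect imputation uncertainty". The LIFEREG template reads "MODEL ttevalue*ttecnsr(1) = trtgrp stratum <covariates>" and has no CLASS statement.

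**The concern.** Membership of the donor cohort depends on something that happens after randomization, but the clock runs from randomization. Section 3 requires follow-up to continue whether or not drug is taken or an event has occurred. Events before the stop, at the stop and after it are therefore all in the database and all enter the fit.

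This can act in two directions. If some nonfatal events lead to stopping, subjects enter the cohort because they had an event, and the fitted hazard rises. Subjects who stop without an event contribute time before the stop during which, given that they were event-free when they stopped, they could not have had one. On-drug deaths may also fall outside the cohort. Both lower the fitted hazard.

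What is at stake is the meaning of the base-case imputation and of F and G. Step 1 motivates the donor cohort by outcome collection both on and off treatment, so a reader will take F and G as multiples of the hazard after stopping. The fit mixes on-drug and off-drug experience.

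A second fault is separate. The Weibull parameters come from one fit and are reused in every draw, so the combining rules cannot reflect uncertainty about them.

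**Working it through.** **No plan figure to reproduce.** The SAP gives no numerical result for this model. The inverse function in 10.4.5 was checked: putting its output back into G returns 0.1, 0.5 and 0.9 for those inputs. The simulation formula is right given the fitted Weibull; the question is what was fitted.

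**What is fitted and what is wanted.** With E for first primary events and Y for time at risk in the donor cohort, and taking crude rates for simplicity:

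- fitted: (E before stop + E after stop) / (Y before stop + Y after stop)
- wanted: E after stop / Y after stop, in subjects event-free at the stop.

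Conditioning on survival past last contact in 10.4.5 does not turn the first into the second, because the fitted distribution already contains the pre-stop terms.

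**Inputs from SAP Section 7:** control rate 3.3% per year; drug discontinuation 6%, 4.5%, then 3% per 6 months.

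**Assumed inputs:** follow-up uniform from 0.3 to 3.5 years; 35% of events fatal; a fatal on-drug event leaves the subject outside the cohort; a nonfatal on-drug event triggers stopping with probability q; post-stop hazard 1, 1.5 or 2 times the on-drug hazard. There were 400,000 subjects per scenario. A Weibull model from randomization was fitted in all discontinuers. Its 1-year hazard from the stop, for subjects event-free then, was divided by the event rate counted from the stop in the same subjects.

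| Post-stop hazard vs on-drug | q = 0 | q = 0.10 | q = 0.25 | q = 0.50 |
|---|---|---|---|---|
| 1× | 0.89 | 1.20 | 1.60 | 2.32 |
| 1.5× | 0.80 | 0.99 | 1.29 | 1.73 |
| 2× | 0.76 | 0.90 | 1.13 | 1.45 |

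Key cases:

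- Highest: 0.0755 / 0.0326 = 2.32.
- Lowest, with nobody who had an earlier event entering the cohort and no fatal events modelled: 0.0219 / 0.0342 = 0.64.
- Two biases cancelling (q = 0.10, 1.5×): 0.0477 / 0.0484 = 0.99.
- No bias (stopping independent of events, none fatal, hazard unchanged): 0.0327 / 0.0329 = 0.99.

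With q above 0, between 34% and 76% of the cohort's events precede the stop. Counting from the stop recovers the true hazard: 0.032 to 0.034 for 0.033; 0.048 to 0.050 for 0.0495; 0.065 to 0.068 for 0.066.

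**Effect on F and G.** A tipping multiplier of 3 on the true post-stop hazard would read as about 3 / 0.64 = 4.7 at one end and 3 / 2.32 = 1.3 at the other. This is approximate, because the control-arm base shifts too.

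**Parameter uncertainty.** Total variance is W + (1 + 1/m)B with m = 1,000, where W is the within-imputation and B the between-imputation variance. Here B arises only from the random event times given one fixed λ and β. The variance of the estimated λ and β enters neither term.

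**Template.** Step 1 asks for three treatment groups, three proton pump inhibitor levels, three CAD/PAD levels and five regions. Without a CLASS statement, numeric codes enter as linear scores, and the comment defines the treatment variable only as 0 or 1.

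**The case against.** **The direction and the cause are not in the SAP.** A reader might infer that the imputed hazard is inflated by events that caused the stop. The SAP does not say that events cause stops; it only fails to exclude them. The trigger share is assumed, and the ratios fall on both sides of 1. This stands.

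**It is not the only check.** Section 10.4.2 compares donors and non-completers descriptively, partly to support the choice of donor cohort. The repeat in all randomized subjects removes the selection on stopping. This stands too, but that repeat supplies no off-drug hazard.

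**The effect on the hazard ratio may be small.** Take 1,100 events split in the Section 4.4 proportions: 826/2 = 413 control and 687/2 = 343.5 in a rivaroxaban arm. Control time is 413/0.033 = 12,515 subject-years. Assume missing time of 2% of that (250 subject-years) in each arm, with equal imputed hazards. Multiplying 0.033 by 0.64 or 2.32 imputes 5.3 or 19.2 events per arm. The event ratio becomes 348.8/418.3 = 0.834 or 362.7/432.2 = 0.839. At an assumed 5% it is 0.837 or 0.849. Section 4.2 expects very few subjects with incomplete follow-up. So the base case is probably robust; the reading of F and G is not. They would regain a clear meaning if absolute imputed rates stood beside them.

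**On-drug deaths.** Table 10-2 compares the last-dose date with the cut-off or the "death date (whatever comes first"), which could suggest that cardiovascular deaths routinely enter the cohort. Section 4.5.1 sets a missing last-dose date to the latest logically possible one, up to the death date, and Table 10-2 counts a last dose on that date as completion. The stronger reading is not supported.

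**Some recipients were lost while on drug.** A post-stop hazard is not self-evidently theirs. But Table 10-2 itself counts every follow-up non-completer as a treatment non-completer, so it fits the plan's own assumption.

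**The template may be shorthand.** The covariate list is a placeholder, and dummy variables could serve. No particular distortion of the arm effects can be claimed, because a three-arm coding is not documented.

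**Conclusion.** The point holds as a fault in one sensitivity analysis. The donor model is selected on later discontinuation and timed from randomization, while its hazard is applied to event-free subjects after last contact. Apart from accidental cancellation, it matches the post-stop hazard only if stopping is unrelated to events and leaves the hazard unchanged, and then there is little reason to prefer this donor cohort.

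The size depends on the assumed trigger share, fatal fraction, follow-up pattern and post-stop hazard; the 0.64 to 2.32 range is illustrative and its direction is open. Holding the parameters fixed contradicts the promise that the pooled inference reflects imputation uncertainty. No size was derived for this, and it will be limited if little follow-up is missing. The missing CLASS statement leaves the template short of Step 1, a minor point.

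A reader might go on to conclude that the tipping-point analysis is worthless or that the primary result is in doubt. The documents support neither: the primary log-rank test does not use this model, and a second imputation model is planned.

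**What to change.** - Fit the donor model from the last-dose date, in subjects event-free at that date, counting first primary events afterwards. Time since discontinuation works with the existing template once the time variable is redefined; left truncation needs an entry time that the template lacks.
- Align the clock in 10.4.5: with time since discontinuation, the censoring time there must be counted from the last dose.
- In each imputation, draw the parameter vector from its estimated sampling distribution before simulating event times.
- Report the absolute imputed event rates by arm beside F and G.
- Code treatment arm, proton pump inhibitor stratum, CAD/PAD and region as categorical, to match Step 1.

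The cost is reprogramming and rerunning one sensitivity analysis. The pantoprazole SAP (Section 1) records that the antithrombotic results have already been reported, so for this trial it would be a supplementary run. The downside is fewer events in the donor model and somewhat wider intervals in this analysis.
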